**Table 5: Event and Censoring Details for Time to First flare/relapse after initial CDA**

Situation	Date of First flare/relapse or Date of Censoring	Censored/ Event
No assessments after first CDA	Date of first CDA	Censored
Flare/relapse before Week 37	Date of first relapse	Event

Situation	Date of First flare/relapse or Date of Censoring	Censored/Event
Rituximab administered	Date of first Rituximab administration	Censored
No flare/relapse during the Blinded Treatment Period	Date of last efficacy assessment during blinded treatment phase (through Week 37)	Censored
Study discontinuation	Date of last efficacy assessment prior to or on the date of treatment discontinuation	Censored
Death before flare/relapse	Date of death	Censored

- Note: Patients will be censored prior to a flare/relapse event should a censoring reason occur. Censoring reasons may be categorized for reporting (e.g. by discontinuation reason). A patient must have a CDA in order to be included in this analysis.
- Complete remission for  $\geq 8$  weeks on zero CS at Week 61 = Yes if complete remission status is achieved at Weeks 53, 57, and 61 with no recorded CS usage during this time; No otherwise, provided all data is complete for the specified visits. For patients with missing data at the specified visits this endpoint value will be missing unless there are a documented CR both before and after the missing visit.
- TEAE = any adverse event with an onset date on or after the first dose of study drug, having been absent pre-treatment or worsening relative to pre-treatment state.
- TEAE (Blinded Treatment Period) = any TEAE with an onset date on or after the first dose of study drug and occurring before enrollment into the open-label portion of the study. TEAEs that are ongoing at the time of enrollment into the open-label portion are considered part of the double-blind portion of the study.
- TEAE (Open-Label Extension Period) = any TEAE with an onset date on or after enrollment into the open-label extension portion of the study, having been absent during the double-blind portion or worsening relative to double-blind portion state. Since the TEAE time is not collected for the study, any AE started or worsened on the first day of the open-label period is considered a TEAE for the blinded treatment period.
- TEAE (Long Term Extension Period) = any TEAE with an onset date on or after enrollment into the long term extension portion of the study, having been absent during the double-blind/open-label extension portion or worsening relative to double-blind/open-label extension portion state. Since the TEAE time is not collected for the study, any AE

started or worsened on the first day of the long term extension period is considered a TEAE for the open-label extension period.

- Treatment duration (days) =

$$\text{Date of last dose of study drug} - \text{Date of first dose of study drug} + 1$$

For subjects who are missing the date of last study drug application, the last visit date will be used in the calculation of treatment duration.

- Study Drug Compliance (%) =

$$\left( \frac{\text{Total number of tablets taken during the treatment}}{\text{Total number of tablets planned during the treatment}} \right) \times 100\%$$

The total number of tablets taken will be calculated by subtracting the number of tablets returned from the number of tablets dispensed. The total number of tablets planned will be calculated by multiplying the total number of days of planned exposure to study drug by 2.

- Corticosteroid compliance (%) = amount (mg) of systemic corticosteroid prescription doses taken divided by amount (mg) of corticosteroid expected to be taken, as collected on the “Prednisone/Prednisolone Accountability” eCRF form.

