CS taper should not begin until ECP has been achieved.

If the first documentation of CDA coincides with no disease activity (PDAI = 0), a follow-up visit  $\geq 2$  weeks later must still confirm that no new lesions are seen and PDAI = 0. At this time the patient is deemed to have confirmed CDA, ECP, and CR and therefore CS tapering can begin. If new lesion(s) are seen, the patient is no longer in CDA and therefore CS tapering should not begin. If a patient has not achieved CDA or new lesions emerge or existing lesions worsen but do not meet definition of relapse/flare, refer to Appendix 1 [Section 12.1](#) regarding increasing steroid dosage.

Throughout the Blinded Treatment Period, patients who fail to respond to treatment or experience a worsening of disease should have their CS dose increased per CS Management Guidelines (Appendix 1 [Section 12.1](#)) until CDA is obtained. If ECP is not achieved in a timely manner, it is encouraged that CS dose be further increased unless clinically contraindicated. The Principal Investigator (PI) should consult with the Medical Monitor in such cases.

Efficacy Outcome Assessment should be performed per the Efficacy Outcome Assessment Flowchart, Appendix 8 [Section 12.8](#).

Once patients achieve CR on a dose of 5 mg/day of CS, that dose should be maintained (not tapered further) until Study Week 37 (time of primary endpoint).

Rituximab treatment may be administered during the Blinded Treatment Period at or after the Week 5 Visit, only after a second “qualifying relapse/flare” occurs, unless contraindicated (Appendix 1 [Section 12.1](#)).

If rituximab is administered, patients should continue to take rilzabrutinib/placebo, remain on trial and blinded to treatment assignment. After completing the Blinded Treatment Period, patients will enter the Open-Label Extension Period to receive active treatment with rilzabrutinib described below. A patient in the Blinded Treatment Period requiring an additional “top up” dose of rituximab after their initial rituximab course of treatment must be discontinued from the trial.

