**Long Term Extension (LTE) Period (Week 61 to Week 109):**

After completing the Open-Label Extension Period, patients who are responding to rilzabrutinib treatment will be eligible to enter the Long Term Extension Period and will continue to receive open-label rilzabrutinib 400 mg bid for 48 weeks per [Table 4](#).

Patients are eligible to participate in the LTE if:

- a) they have achieved and/or maintained an ECP with  $\leq 10$  mg/day CS at any time between 37 and 61 weeks in the study.

Patients are not eligible to participate in the LTE if:

- a) they have more than one relapse/flare following ECP requiring treatment with  $> 10$  mg/day CS (excluding CS taken short-term for dental work or surgery), or
- b) have failed to adequately recover after a relapse/flare despite maximal tolerated CS dose.

Failure to adequately recover is defined as:  $< 25\%$  decrease from peak PDAI despite treatment with maximal steroid doses (minimum of 1.5 mg/kg/day unless there is a specific documented medical contraindication) for at least 2 weeks.

CS doses above refer to doses of prednisone or its equivalent.

Patients may continue in the LTE until:

- a) they have had more than one relapse/flare following ECP that requires  $> 10$  mg/day CS (excluding CS taken short-term for dental work or surgery) or have failed to adequately recover after a relapse/flare despite maximal tolerated CS dose (per definition of failure to adequately recover above);
- b) the drug is no longer being developed by the Sponsor for this indication;
- c) the program is stopped for safety reasons.

Patients who have previously completed the Open-Label Extension Period prior to this amendment and were responders per the LTE requirement may enroll into the LTE.

Patients entering the LTE will receive Sponsor-provided CS, following CS Management Guidelines (Appendix 1 [Section 12.1](#)).

Patients requiring rituximab during the Long Term Extension Period will be discontinued from the trial.

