### **Open-Label Extension Period (Weeks 37 to 61)**

From Week 37, all patients will receive active drug in the Open-Label Extension Period for 24 weeks per [Table 3](#). Patients who received placebo will thus receive active treatment with rilzabrutinib 400 mg bid. Patients requiring treatment by rituximab or other immunosuppressants (other than CS) for relapse/flare during this period, must be discontinued from the study. If a patient has a qualifying relapse/flare during the Blinded Treatment Period and the second infusion from the rituximab course of treatment occurs during the Open-Label Extension period, the patient may continue in the trial.

Patients that received rituximab during the Blinded Treatment Period and are continuing in the study, will complete TBNK testing (T and B and Natural Killer Lymphocyte Panel) at their Week 37 Visit.

From Week 37 (time of primary endpoint), further tapering to 0 mg CS should be attempted in patients with CR unless medically contraindicated. Patients who fail to respond to treatment or experience worsening of disease should have their CS dose increased per CS management guidelines (Appendix 1 [Section 12.1](#)) until CDA is obtained. If ECP is not achieved in a timely manner, it is encouraged that CS dose be further increased unless clinically contraindicated. The PI should consult with the Medical Monitor in such cases.

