#### **Rituximab and Possible Combination with rilzabrutinib**

Rituximab is a chimeric anti-CD20 antibody authorized for the treatment of rheumatoid arthritis, non-Hodgkin’s lymphoma, chronic lymphocytic leukemia (CLL), and granulomatosis with polyangiitis (granulomatosis with polyangiitis [GPA] also known as Wegener’s granulomatosis) and microscopic polyangiitis (MPA) in combination with CS. An open-label, randomized study comparing rituximab with 0.5 to 1 mg/kg/day of prednisone with 1 to 1.5 mg/kg/day of prednisone found a CR rate of 89% could be achieved by two years compared with 34% for CS alone. The study used a regimen of treatment at Month 0 of two 1 g infusions, two weeks apart, and 500 mg each at Month 12 and 18 (11). Although it is approved for the treatment of pemphigus only in the US at this time, it is recommended as a possible first-line therapy in combination with CS in newly updated consensus guidelines (1).

RITUXAN, MabThera or other approved, biosimilar agents may be used in this clinical trial per protocol. Instructions for administration of the intravenous infusion will be provided in the Pharmacy Manual. For detailed safety information on rituximab or other biosimilar agents investigators should refer to the current, locally applicable, approved product information.

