### 9.3.5 Efficacy analysis (mITT Population)

In general, the need for rituximab rescue will be considered “treatment failure” for the analysis of efficacy endpoints except cumulative CS and composite GTI score.

The analyses for efficacy endpoints involving clinical assessment of CR during the blinded treatment period will be performed based on data collected during on-site visits (i.e., not including data collected from remote visits) as the primary analyses.

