**Table 4: Event and Censoring Details for Time to First CR with a CS dose at or below 10 mg/day**

Situation	Date of First CR/ Date of Censoring	Censored/ Event
No post baseline assessments	Date of first dose	Censored
Patient in CR status and with a CS dose of $\leq 10$ mg/day	First date that patient is in CR status and with a CS dose of $\leq 10$ mg/day as identified in Section 6.1.9.	Event
Rituximab administered	Date of first Rituximab administration	Censored
No CR with a CS dose of $\leq 10$ mg/day during the Blinded Treatment Period	Date of last efficacy assessment during blinded treatment phase (through Week 37)	Censored
Study discontinuation	Date of last efficacy assessment prior to or on the date of treatment discontinuation	Censored
Death before CR	Date of death	Censored

Note: Patients will be censored prior to a CR event at the earliest date of the censored events above should a censoring reason occur. Censoring reasons may be categorized for reporting (eg, by discontinuation reason).

- Three or more lesions within 1 month that do not heal spontaneously within 1 week or extension of established lesions = Yes if any of the following conditions are satisfied:
  - eCRF entry “Have new lesions appeared within a month that did not heal spontaneously within 1 week? OR Have there been extension of established lesions?” = Yes for any visits from Baseline up to Week 37.
  - At this visit, Has a Relapse occurred or is continuing?

The number of instances with investigator assessments of disease worsening will also be derived and categorized for reporting as 0, 1, 2, and  $\geq 3$ . After the first worsening, a patient can have additional worsening, but only after the patient returns to CDA first, and then the next worsening can happen.

- PDAI score  $< 3$  from Week 29 to Week 37 with a CS dose of  $\leq 10$  mg/day = Yes if the following conditions are both satisfied:
  - PDAI  $< 3$  = Yes for all visits from Week 29 through Week 37
  - Daily prednisone dose is  $\leq 10$  mg/day from Week 29 through Week 37 as defined in Section 6.1.9.
  - No Rituximab therapy prior to Week 37.

After applying the CS dose imputation as described in Section 6.1.5.2, a patient with partial missing data (missing PDAI assessment or CS dose) or complete missing data at any scheduled visit will be considered as a non-responder.

- Change from baseline = value at current time point – value at Baseline.

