## 11. Other Planned Analysis

### 11.1. Pharmacokinetic and Pharmacodynamic Analysis

Individual and group PK (PRN1008 and metabolites as applicable) and PD (anti-desmoglein-1 and -3) data will be summarized, displayed graphically, and by descriptive statistics for each visit, where measured. Additional analyses may be described and reported separately.

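### The Week 61 steroid-free remission derivation in SAP 6.1.8 has no rituximab condition, so remissions after rescue count as remission on rilzabrutinib, against Protocol 9.3.5

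*SAP*

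**What the plan says.** **Rescued patients stay in.** Protocol 1.1 and 4.1: "If rituximab is administered, patients should continue to take rilzabrutinib/placebo, remain on trial and blinded to treatment assignment". After that, "From Week 37, all patients will receive active drug in the Open-Label Extension Period for 24 weeks". A second infusion may fall in the open-label period if the qualifying flare was in the blinded period. A new need for rituximab in the extension means discontinuation, so the exposure at issue comes from blinded-period rescue.

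**The protocol's rule.** Section 9.3.5: "In general, the need for rituximab rescue will be considered" a failure of treatment for efficacy endpoints. Cumulative CS dose and the GTI composite are excepted. The rule has no Week 37 limit.

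**The SAP's Week 61 derivation (6.1.8).** The patient is "Yes if complete remission status is achieved at Weeks 53, 57, and 61 with no recorded CS usage during this time". Nothing about rituximab follows. In the same section, the PDAI below 3 derivation carries the condition "No Rituximab therapy prior to Week 37", and Tables 4 and 5 censor at the first infusion.

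**Where SAP 6.1.5.2 has a rule to Week 61.** Time to first CR is censored at rituximab. PDAI, ABQOL and EQ-5D-5L changes use only data from before rituximab. ABQOL of zero counts as non-response from the first infusion.

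**Where no rule is visible.** Cumulative CR duration for Weeks 37 to 61 (8.3 and Table 6), relapse after CR (8.4), the long-term extension (LTE) summaries (9.7), and anti-desmoglein, where 11.1 says only that "data will be summarized, displayed graphically, and by descriptive statistics for each visit, where measured".

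**The concern.** The Week 53 to 61 proportions serve the objective on longer-term durability of remission. They are reported for each original randomised group, and SAP 4.1 also calls for open-label results overall. A reader will take them as steroid-free remission on rilzabrutinib. A patient who flared twice, was rescued and then remitted is a failure under Protocol 9.3.5 but a success under SAP 6.1.8.

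CR duration for Weeks 37 to 61 is compared between original groups with a zero-inflated negative binomial model. If rilzabrutinib works, more placebo patients should need rescue. Their later CR days would then be credited to the placebo-origin group and would distort that contrast.

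The protocol itself recognises carry-over. At entry it requires six months since anti-CD20 treatment, or documented B-cell reconstitution, and it orders a lymphocyte panel at Week 37 in rescued patients.

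**Working it through.** No sample size, power or alpha figure is at issue. The check has three steps.

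**1. Timing.** SAP Table 3 puts Week 53 at Day 365 and Week 61 at Day 421. The difference is 56 days, or 8 weeks, which matches the endpoint's label. By the qualifying-flare route, rescue can start from the Week 5 visit. For a first infusion between Week 5 and Week 37, the Week 53 to 61 window lies between 53 − 37 = 16 and 61 − 5 = 56 weeks later.

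**2. One patient under each text.** Take a patient given rituximab at Week 25 who is in CR without CS at Weeks 53, 57 and 61.
- Protocol 9.3.5: failure.
- SAP 6.1.5.2, time to first CR to Week 61: censored at the infusion, unless CR on 10 mg/day or less came first.
- SAP 6.1.5.2, ABQOL of zero at Week 61: non-responder.
- SAP 6.1.8, CR on zero CS at Week 61: Yes.

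The last result disagrees with the others, and the line that produces it is complete and unredacted.

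**3. Size.** Let r be the proportion of evaluable patients rescued, q the zero-CS CR rate in rescued patients, and p the rate in the rest.
- As written: r·q + (1 − r)·p
- Rescue counted as failure: (1 − r)·p
- Difference: r·q, whatever p is

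The documents give none of these. I assume r of 5% to 20%. For q I use 34% and 89%, from the rituximab study in Protocol 4.3, which "found a CR rate of 89% could be achieved by two years compared with 34% for CS alone". Both are two-year CR rates and not zero-CS rates at Weeks 53 to 61, so they only mark a range.

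| Rescue rate r | q = 34% | q = 89% |
|---|---|---|
| 5% | 1.7 points | 4.5 points |
| 10% | 3.4 points | 8.9 points |
| 20% | 6.8 points | 17.8 points |

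Example with r = 10%, q = 89% and an assumed p = 30%:
- as written: 0.10 × 0.89 + 0.90 × 0.30 = 35.9%
- rescue as failure: 0.90 × 0.30 = 27.0%
- share of counted remissions from rescued patients: 0.089 / 0.359 = 25%, or 60 × 0.089 = 5.3 patients in a group of 60

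Unequal rescue, with assumed counts of 6 of 60 on placebo and 2 of 60 on rilzabrutinib and q = 60%:
- placebo-origin: 6 × 0.60 / 60 = 6.0 points
- rilzabrutinib-origin: 2 × 0.60 / 60 = 2.0 points
- net: 4.0 points in favour of the placebo-origin group

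**The case against.** **The protocol already covers the CR endpoints.** Section 9.3.5 is general, and SAP Section 10 declares no changes from the planned analysis. This stands in part: for CR the defect is a protocol rule not carried into the derivation, not the lack of any rule. But the protocol makes the SAP the final authority on analysis, and a programmer following 6.1.8 would count the rescued remission. Anti-desmoglein is a pharmacodynamic endpoint, outside the rule altogether.

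**Redaction.** Much of SAP 6.1.5.1 is blacked out, and the CS-dose derivation in 6.1.9 is not fully visible. SAP Table 1 says imputation of CS and CR status was extended to other endpoints. A rule for CR duration may therefore exist unseen. The Week 61 derivation and 11.1 show no redaction.

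**Low stakes.** The Week 53 to 61 proportions are exploratory and carry no randomised comparison. The primary endpoint and the key secondary testing sequence are not affected by this point. That stands, and it limits the consequence.

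**Counting rescue as failure is a choice.** Rescued patients also take rilzabrutinib, so not all of their remission is artefact. That is fair: r·q measures the gap between two counting rules, not proven bias. But the protocol has already chosen one of them.

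**How long one course acts.** The documents do not say. If the six-month entry washout is read as the duration, then 26 weeks from the second infusion (two weeks after the first) reaches Week 53 only when the first infusion was at about Week 25 or later (53 − 26 − 2 = 25).

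**Conclusion.** The derivation conflicts with Protocol 9.3.5 and with the SAP's own handling of neighbouring endpoints, and it should be corrected. The inflation is r·q: 3.4 to 8.9 points if 10% are rescued and 34% to 89% of those are in zero-CS CR. These are assumptions, and the true size cannot be derived from the documents.

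Four wider readings are tempting and are not supported:
- **That the SAP loses track of rescued patients throughout the open-label period.** Time to first CR, PDAI, ABQOL and EQ-5D-5L have explicit rules to Week 61.
- **That the LTE is broadly affected.** The protocol says "patients who are responding to rilzabrutinib treatment will be eligible to enter the Long Term Extension Period", and its entry criterion does not mention rituximab. But more than one flare after ECP needing over 10 mg/day CS bars entry, and the main rescue route requires a second qualifying flare after ECP. Many rescued patients would be excluded. The route for patients who never reach disease control stays open, and the counting window for the bar is not stated.
- **That titre falls after rituximab always favour rilzabrutinib.** At Weeks 25 and 37, rescue in the placebo group would lower placebo titres and so work against rilzabrutinib.
- **That 89% is the rate to expect here.** It comes from a regimen with further infusions at Months 12 and 18. This trial allows one course.

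**What to change.** 1. In SAP 6.1.8, add to the Week 61 zero-CS CR derivation the condition that no rituximab has been received, so that a rescued patient is No.
2. In SAP 8.3 and Table 6, count no CR days from the first infusion in the CR-duration endpoints whose window runs past Week 37. Both changes follow Protocol 9.3.5.
3. For anti-desmoglein (11.1), relapse (8.4, 9.7) and LTE CS dose (9.7), keep the all-patient summary and add one that shows rituximab-exposed patients separately, so that results can be read with and without them.

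A blanket non-responder rule would not suit item 3. It has no meaning for average dose or time to relapse, and Protocol 9.3.5 exempts cumulative CS. Dropping antibody values after rescue would also create informative missingness.

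The cost is SAP wording, a slightly lower reported open-label remission rate and a few table rows. The date of first rituximab is already used elsewhere in the SAP. No clinical rule changes.

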#### **Open-Label Extension Period (Weeks 37 to 61):**

From Week 37, all patients will receive active drug in the Open-Label Extension Period for 24 weeks per [Table 3](#). Patients who received placebo will thus receive active treatment with rilzabrutinib 400 mg bid. Patients requiring treatment by rituximab or other immunosuppressants (other than CS) for relapse/flare during this period, must be discontinued from the study. If a patient has a qualifying relapse/flare during the Blinded Treatment Period and the second infusion from the rituximab course of treatment occurs during the Open-Label Extension period, the patient may continue in the trial.

Patients that received rituximab during the Blinded Treatment Period and are continuing in the study, will complete TBNK testing (T and B and Natural Killer Lymphocyte Panel) at their Week 37 Visit.

From Week 37 (time of primary endpoint), further tapering to 0 mg CS should be attempted in patients with CR unless medically contraindicated. Patients who fail to respond to treatment or experience worsening of disease should have their CS dose increased per CS management guidelines (Appendix 1 [Section 12.1](#)) until CDA is obtained. If ECP is not achieved in a timely manner, it is encouraged that CS dose be further increased unless clinically contraindicated. The PI should consult with the Medical Monitor in such cases.

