### 2.3.4. Exploratory Endpoints

Exploratory endpoints and analyses include the following:

- Exploratory PK/PD analysis will examine the effects, if any, of covariates on PK and/or PD, and the relationship between PK, PD and efficacy in this population
- Number and type of hospitalizations, outpatient medical visits, concomitant medication use, adverse events and other relevant outcomes
- Change from baseline in PDAI by visit and the temporal relationship to changes in quality of life and health economic variables
- Proportion of patients with relapse after achievement of CR between Baseline and Week 61, and between Baseline and Week 109
- Proportion of patients initially randomized to PRN1008 that are in CR with a zero CS dose, from Week 53 to Week 61 (no randomized treatment comparison)
- Proportion of patients initially randomized to placebo that are in CR with a zero CS dose, from Week 53 to Week 61 (no randomized treatment comparison)
- Change in Treatment of Autoimmune Bullous Disease Quality of Life (TABQOL) score from Baseline to Weeks 5, 13, 25, 37, 61, and 109
- Total number of disease flares/relapses from Week 37 to Week 61, and from Week 61 to Week 109
- (Optional) Blood samples for exploratory analysis of vaccine IgG response during treatment.

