#### 6.1.5.1. Imputation Procedures for the Primary Efficacy Endpoint

For the primary efficacy endpoint (the proportion of patients who are in CR from Week 29 to Week 37 with a prednisone dose of  $\leq 10$  mg/day), patients with missing data due to study withdrawal will be considered as non-responders. A patient who received a rituximab dose prior to Week 37 will also be counted as a non-responder. [REDACTED]

[REDACTED]

- [REDACTED]
- [REDACTED]

[REDACTED]

[REDACTED]

[REDACTED]

[figure not shown]
[REDACTED]

[REDACTED]

Tipping point analyses (Yan, 2009) will be done to investigate the impact of missing data and lost to follow-up (LTF). The tipping point analysis will look at all possible combination of

converting missing data to a responder, starting at 0 and ending at all are responders. The cases where the statistical significance tips from significance to non-significance (defined as a two sided p-value  $>0.05$ ) will be listed. A complete list of all combinations will also be presented. If the imbalances that leads to a change in interpretation are clinically implausible then the results of the primary analysis will be deemed reliable

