#### 8.4. Exploratory Analyses

The number and percentage of patients with relapse after achievement of CR through Week 61 (Yes/No) will be presented by treatment group. A similar summary will be presented for patients that reached CR with a zero CS dose by from Week 53 to Week 61 (Yes/No).

Observed values and changes from Baseline in Treatment of Autoimmune Bullous Disease Quality of Life (TABQOL) will be presented at each study visit based on summary statistics by treatment group. Descriptive summaries for the Open-Label and Long Term Extension periods will report data by treatment group in double-blinded portion and overall.

The total number of disease flares/relapses from initial Week 37 to Week 61 will be analyzed based on the same methodology described for the cumulative duration of CR with CS dose  $\leq 10$ mg/day from Baseline to Week 37 in Section 8.2, using an offset term representing the time of patient participation in the Open-Label Treatment Period.

During the COVID-19 pandemic, measures to ensure continued drug supply and safety monitoring for patients were implemented. In-clinic study visits, as outlined in the protocol schedule of assessments, may be changed to a remote visit (e.g., telephone call, video call) as needed to address the COVID-19 restrictions. As a result, statistical analyses of efficacy endpoints involving CR assessment for the blinded treatment period will not include data collected from these remote visits. The incidence of remote visits and the corresponding reason for missing the onsite visits will be summarized by visit. Supportive analysis will be performed by including data collected remotely.

The analyses of the following endpoints will be documented and reported separately:

- Exploratory PK/PD analysis will examine the effects, if any, of covariates on PK and/or PD, and the relationship between PK, PD and efficacy in this population
- Cost utilities based on the number and type of hospitalizations, outpatient medical visits, concomitant medication use, adverse events and other relevant outcomes
- the temporal relationship of change in PDAI with changes in quality of life and health economic variables.

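### The Week 61 steroid-free remission endpoint scores some known failures as missing, and its denominator is not stated

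*SAP*

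**What the plan says.** SAP 2.3.4 lists among the exploratory endpoints "Proportion of patients initially randomized to PRN1008 that are in CR with a zero CS dose, from Week 53 to Week 61", with a matching item for the placebo arm. Both are marked as having no randomized comparison. SAP 8.4 reports the result as a number and percentage (Yes/No) by treatment group and does not name the denominator.

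The derivation is in SAP 6.1.8, in the list after Table 5. Yes requires CR at Weeks 53, 57 and 61 with no CS recorded over that time. The rule for the rest is "No otherwise, provided all data is complete for the specified visits". Incomplete patients are handled by "For patients with missing data at the specified visits this endpoint value will be missing". The one exception is a gap that has documented remission on each side of it.

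For the open-label period, Protocol 4.1 states: "Patients requiring treatment by rituximab or other immunosuppressants (other than CS) for relapse/flare during this period, must be discontinued from the study".

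Other responder endpoints are treated differently. For the primary endpoint, SAP 6.1.5.1 says "patients with missing data due to study withdrawal will be considered as non-responders", and a rituximab dose before Week 37 is also non-response. For PDAI below 3 over Weeks 29 to 37, SAP 6.1.8 makes a patient with missing data at any scheduled visit a non-responder. Protocol 9.3.5 treats the need for rituximab as treatment failure in general, with cumulative CS and composite GTI as the only exceptions.

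**The concern.** The endpoint asks whether remission without CS was held from Week 53 to Week 61. One documented visit out of CR, or any CS use in that window, settles the answer as No. The rule ignores this unless the other visits were also attended. The only gap it fills is one between two documented remissions, and it fills that gap towards success. No clause lets an incomplete patient be scored a failure.

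Part of the missingness is also tied to failure by design. A patient whose relapse needs rituximab or another immunosuppressant has to leave the study, and so has no later visits and no later CR to bridge to.

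At stake is a reported percentage in each original arm that bears on the objective of longer-term durability of CR. Although no test is planned, the two percentages will be read side by side.

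**Working it through.** **Step 1. Apply the rule to visit patterns.** C = in CR, N = not in CR, dot = visit missing. Assume CR at Week 49, no assessment after Week 61 and no recorded CS.

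| Weeks 53 / 57 / 61 | Score under SAP 6.1.8 | Is the true answer already settled? |
|---|---|---|
| C C C | Yes | Yes |
| C N C | No | No |
| C . C | Yes (bridged) | not settled |
| N . . | missing | No |
| C N . | missing | No |
| C . . | missing | not settled |
| C C . | missing | not settled |
| . . . | missing | depends on why the patient left |

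The N . . and C N . patterns are certain failures scored as missing. The same happens to a patient with CS recorded in the window and one unbridged missed visit. The last row includes patients discontinued before Week 53 for a relapse needing rituximab or another immunosuppressant.

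**Step 2. Look for another rule that corrects this.** The introduction to SAP 6.1.5 covers primary and secondary endpoints. The rituximab rules visible in 6.1.5.2 do not list this endpoint. SAP Table 1 says that similar imputation was extended to exploratory endpoints in version 2, but that is a change log, and the current derivation in 6.1.8 does not show it. No visible operative text turns these patients into failures.

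**Step 3. Size.** The plan gives no response, dropout or power figure for this endpoint, so there is nothing to reproduce. Inputs: n = 60 per original arm (approximate, Protocol 4.1). The number of Yes, x, and the number missing, m, are assumptions.

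- Whole-arm percentage: x/n
- Percentage of non-missing values: x/(n − m)
- Ratio: n/(n − m) = 1/(1 − m/n)

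| m (of 60) | Ratio | x = 12 (whole arm 20.0%) | x = 18 (whole arm 30.0%) |
|---|---|---|---|
| 3 (5%) | 1.05 | 12/57 = 21.1% | 18/57 = 31.6% |
| 6 (10%) | 1.11 | 12/54 = 22.2% | 18/54 = 33.3% |
| 12 (20%) | 1.25 | 12/48 = 25.0% | 18/48 = 37.5% |
| 18 (30%) | 1.43 | 12/42 = 28.6% | 18/42 = 42.9% |
| 24 (40%) | 1.67 | 12/36 = 33.3% | 18/36 = 50.0% |

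These ratios compare with a denominator that keeps every missing patient. If only some of them are known failures, the misclassification explains only part of the gap. With x = 12, m = 12 and 6 of the 12 known failures, rescoring those 6 as No moves the non-missing percentage from 12/48 = 25.0% to 12/54 = 22.2%. The whole-arm figure is 20.0%.

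**Step 4. Unequal exits.** With 12 Yes in each arm of 60 and 6 versus 18 missing, the non-missing percentages are 12/54 = 22.2% and 12/42 = 28.6%, although the same number succeeded in each arm.

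**The case against.** The strongest reply concerns the denominator. A reader might infer that these patients certainly leave it and that the proportion is certainly overstated. The documents do not say so. SAP 2.3.4 words the endpoint as a proportion of patients initially randomized to each arm. SAP 8 puts all efficacy analyses on the mITT population. SAP 4.1 mentions non-missing counts for continuous summaries, not for categorical ones. All of this fits a whole-arm denominator, under which the Yes percentage is the same whether these patients are labelled missing or No. This stands: inflation is conditional. Labelling certain failures as missing is wrong under either denominator.

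A reader might also infer that every relapse leads to exit. It does not. Relapse managed with CS keeps the patient in the study, and with complete visits and CS recorded in the window that patient scores No. The group lost through mandatory discontinuation is a subset of unknown size.

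Nor is this the main measure of durability. It is one exploratory item among several, and the cumulative CR duration endpoints, which rank as other secondary, address the same objective.

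Two further points limit the remedy. Not every missing value is a failure: visits may be missed because of COVID-19 restrictions (Protocol Appendix 9), and participants in Germany must stop after a positive SARS-CoV-2 test (Appendix 10). Parts of SAP 6.1.5.1 are also blacked out, so a hidden rule on CR status cannot be excluded. If one exists, the wording in 6.1.8 still contradicts it and needs correcting.

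**Conclusion.** The rule in SAP 6.1.8 is wrong as written for two groups. The first is patients with documented non-CR or CS use in Weeks 53 to 61 who miss another visit. The second is patients discontinued in the open-label period, before Week 61, because a relapse needs rituximab or another immunosuppressant. For the first group No is certain. For the second, Protocol 9.3.5 supports failure directly where rituximab is needed; for other immunosuppressants the argument is that the same mandatory exit for relapse applies.

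The numerical effect depends on a denominator that the SAP leaves unstated. With non-missing values the percentage is inflated by 1/(1 − m/n), for example 1.11 at 10% missing and 1.25 at 20%. With the whole arm it is not inflated. The missing rates are assumptions. The endpoint is exploratory and non-comparative, so the primary and key secondary tests and the type I error are untouched. The documents do not support a claim of definite overstatement, or a rule that every missing value counts as failure.

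**What to change.** Revise the derivation in SAP 6.1.8 and the reporting in 8.4:

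- Score No for any observed visit out of CR, or any recorded CS use, in Weeks 53 to 61, whether or not the other visits are complete.
- Score No for any receipt of rituximab or another immunosuppressant before Week 61, and for discontinuation before Week 61 because one was needed. As worded, this includes rituximab given in the blinded period to patients who continue, in line with Protocol 9.3.5.
- Keep the bridging exception.
- State a fixed denominator: mITT patients by original arm, to match the endpoint's reference to patients initially randomized. This includes patients who never entered the open-label period, so the table should say so.
- Show the remaining missing values as their own category within that denominator, and give the observed-case percentage as a supplement.

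The cost is SAP wording and minor programming. No new data are needed and patient management does not change. The downside is that the reported proportion may be slightly less favourable.
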